#### **11.** INVESTIGATIONAL PRODUCTS

In this study, no investigational products will be used.

#### 12. OTHER

#### 12.1 Funding

This study is funded by the European and Developing Countries Clinical Trials Partnership (EDCTP). The main funding contract is between EDCTP and the UoL IGH (grant number EDCTP-CSA MI -2014-592) and by subcontract between UoL IGH and RU and UoL IGH and ITM.

#### 12.2 Study management and oversight

The trial sponsor is UoL and this protocol and other study documentation was therefore reviewed and approved by the UoL Sponsorship Committee. Overall study management at UoL will be coordinated by the Chief Investigator [name] in the Institute of Infection and Global Health. She will make use of resources available through the UoL Research Support Office.

Study implementation in Rwanda will be managed by the RU team, led by the Principal Investigator [name]. He will work closely with the RU community outreach, clinical, laboratory, data management, and social science team leaders. All clinical and qualitative research procedures (with the possible exception of the IDI's with stakeholders), as well as diagnostic laboratory testing, will take place at RU according to RU SOPs and using RU source documents.

#### 12.3 Protocol amendments

This study will be conducted in full compliance with the most recent approved version of the study protocol. Protocol amendments will be reviewed and approved by the investigators and ethical review committees prior to implementing the amendment, except when necessary to protect the safety, rights and wellbeing of study participants.

#### 12.4 Good clinical practice

This study will be implemented in accordance with the ICH-Good Clinical Practice (GCP) and Good Clinical Laboratory Practice (GCLP) guidelines. We will implement the following monitoring procedures:

- The Chief Investigator will travel to Kigali to conduct the study training and study initiation visit.
- During implementation of the demonstration project, daily internal quality control procedures will be implemented in accordance with the RU SOP for Data Management and Quality Control (which is based on ICH-GC(L)P).
- A UoL project manager will conduct two monitoring visits during implementation of the demonstration project.
- The Chief Investigator will travel to Kigali again to conduct the study close-out visit.

#### 12.5 Study termination

If the study is prematurely terminated or suspended, the Chief Investigator will promptly inform the investigators/institutions involved in the study, the ethics committees listed in section 10.1, the Rwanda National Research Committee, and the Rwanda Ministry of Health of the termination or suspension and the reason(s) for the termination or suspension. The RU Principal Investigator is responsible for informing active study participants of study termination or suspension.

#### 12.6 Dissemination of results

Findings from this project will be disseminated at a workshop in Kigali after the completion of the study as described in section 7. They will also be presented at national and international conferences, and published in peer-reviewed journals. Findings will be reported back to the study participants and their communities by RU staff with the help of the community mobilisers.

#### 12.7 Archiving

Study records and data will be kept at RU according to the RU SOP for Archiving. RU will retain all

study records and data until all data analyses and report-writing have been completed, after which they will be destroyed. Study records and data may not be destroyed without prior written approval from the Chief Investigator.

After database lock, all anonymised study data will also be kept on the UoL M-drive (under the custodianship of the Chief Investigator) until all data analyses and report-writing has been completed. After that, the anonymised study data will be archived in the UoL RDM DataStore (https://www.liverpool.ac.uk/csd/research-data-management/).

All data generated in this project will be co-owned by RU and UoL. However, after database lock, the anonymised data will be shared with project partner ITM Antwerp and with the Ministry of Health in Rwanda. The anonymised data may also be made available to other interested parties using RDM DataStore facilities on a case-by-case basis. The ePIR will never be shared with third parties to protect participant confidentiality.

#### 14. APPENDICES

#### 14.1 Schedule of assessments

Procedures	Main visit	Additional visits	IDI
Informed consent	Х		Х
Assign PIN and contact information	Х		Х
Eligibility checklist	Х		
Face-to-face interview incl. risk scoring/symptoms, quantitative	Х		
Face-to-face interview, qualitative			Х
Offer services and ask women if they want to opt out of any services	Х	X1	
HIV/STI/BV risk reduction counselling	Х	[X]	
If not opted out: Venepuncture (10 ml) or finger prick	Х		

 
Rapid HIV testing
 
	Х		

 
If pregnant or selected by risk scoring: Syphilis POCT
 
	Х		
If not opted out and indicated: Urine collection	Х		

 
If indicated: hCG urine pregnancy testing
 
	Х		

 
If UTI symptoms: Urinalysis dipstick testing
 
	Х		
If not opted out: Collection of vaginal swabs without speculum	Х		
(choose if self-sampling or clinician-sampling)			

 
Vaginal pH and TV POCT
 
	Х		

 
If selected by risk scoring: CT/NG POCT
 
	Х		
Gynaecological exam 	[X]	[X]	
Provide POCT results	Х	Х	
Provide treatment based on POCT results and management of genital	[X]	[X]	
ulcers/inguinal bubos, vaginal candidiasis and lower abdominal pain if			
relevant symptoms reported			
Provide partner notification and treatment		[X]	
Provide referrals	[X]	[X]	
Client satisfaction survey (on a subsample)	Х		
Laboratory procedures at end of study			
Vaginal swabs:			
- CT/NG POCT on stored samples from women who were not	Х		
tested before			
- If funding permits: NG, CT, TV, BV PCRs on all stored samples	Х		
Left-over urine:			

 
If funding permits: molecular testing of stored samples to determine organisms associated with UTIs
 
	Х		

BV=bacterial vaginosis; CT=*Chlamydia trachomatis*; FU=follow=up; hCG=human chorionic gonadotropin; IDI=in depth interview; NG=*Neisseria gonorrhoeae*; PIN=participant identification number; PCR=polymerase chain reaction; POCT=point-of-care test; STI=sexually transmitted infection; UTI=urinary tract infection; TV=*Trichomonas vaginalis*. [x] = only if indicated.

1. Only procedures for which the visit was intended will be carried out.

2. By the algorithm recommended in the most recent Rwandan HIV voluntary counselling and testing guidelines.

3. Gynaecological exams will only be done when deemed necessary by the study physician (for example, in the case of genital ulcers or lower abdominal pain).

#### 14.2 WISH clinical algorithms

See attached as a separate document

#### **14.3 WISH treatment guidelines by etiologic or syndromic diagnosis** See attached as a separate document

# **Appendix 14.2: WISH clinical algorithms**

CT= *Chlamydia trachomatis*; NG= *Neisseria gonorrhoeae*; pH=vaginal pH; PID=pelvic inflammatory disease; POCT=point of care test; syph=syphilis; TV= *Trichomonas vaginalis*.

#### APPENDIX 14.3: WISH TREATMENT GUIDELINES BY ETIOLOGIC OR SYNDROMIC DIAGNOSIS

Diagnosis	Treatment (follow latest Rwandan guidelines)	Other Follow-Up
Gonorrhea Positive GeneXpert NG test. Treat regardless of the presence of symptoms.	1 st choice: Ciprofloxacin 1g single oral dose 2 nd choice: Ceftriaxone 250 mg in one single IM dose	
 
In female sex workers, also consider the possibility of rectal or pharyngeal NG (take throat and rectal swabs for testing if suspected).
 
Actively follow-up participants with laboratory-confirmed NG approximately 7 days after treatment to check for treatment failure (due to NG resistance). If symptoms are still reported, give the 2nd choice treatment.
 
Male partners should be treated in the same manner as the female index case. Couples should be treated around the same time and counseled to abstain from sex or use condoms during treatment to avoid re-infections.
 

Chlamydia Positive GeneXpert CT test.	1 st choice: Doxycyclin 100 mg twice per day for 7 days 2 nd choice: Erythromycin 1g twice per day for 7 days	
 
Most CT infections are asymptomatic so active follow-up after treatment is not useful.
 
Male partners should be treated in the same manner as the female index
 

Treat regardless of the presence of symptoms.		case. Couples should be treated around the same time and counseled to abstain from sex or use condoms during treatment to avoid re-infections.
Trichomoniasis Positive TV OSOM test. Treat regardless of the presence of symptoms.	
 
1st choice: Metronidazole 2 g single oral dose
 
OR Metronidazole 400 or 500 mg orally twice per day for 7 days
 
2nd choice: Tinidazole 2g single oral dose OR Tinidazole 500 mg twice per day for 7 days
 
	
 
If BV is also present (see below), the 7 day treatment is preferred because it is more effective against BV. However, if poor adherence is suspected, use a single dose treatment.
 
Male partners should also be treated in the same manner as the female index case. Couples should be treated around the same time and counseled to abstain from sex or use condoms during treatment to avoid re-infections.
 

Bacterial vaginosis Vaginal pH is 5.0 or higher. Treat regardless of the presence of symptoms.	
 
1st choice: Metronidazole 400 or 500 mg orally twice per day for 7 days OR Metronidazole 2g single oral dose.
 
2nd choice: Tinidazole 2g orally once a day for 2 days or 1g per day for 5 days.
 
Alternative: Clindamycin 300 mg orally twice per day for 7 days
 
	
 
Metronidazole 2g single oral dose is a less effective treatment for BV than the 7-day treatment. Only give a single oral dose if you are worried that the patient will not be adherent for 7 days.
 
Women should be encouraged to wear clean underwear daily, not wash inside the vagina (and if this cannot be avoided, to use clean plain water only), and use hormonal contraception to prevent recurrence.
 
Male partners are not treated but women should be told that BV-associated bacteria can be passed between sexual partners. Their male partners should be encouraged to improve their penile hygiene and clean underneath the foreskin regularly.
 

Vaginal candidiasis When symptoms typical for vaginal candidiasis are present: White, curd-like, odorless vaginal discharge with vaginal itching and/or burning.	
 
1st choice: Fluconazole 150 mg single oral dose
 
2nd choice: Clotrimazole 200 mg pessaries every night for 3 nights
 
	
 
Do not treat without lab confirmation; do not treat if asymptomatic)
 
Male partners are not notified but if a male partner has symptoms of balanoprosthitis, he can be given 1% Clotrimazole cream to be applied for 14 days.
 
Patients should be counseled to abstain from sex or use condoms, until symptoms have cleared.
 

Diagnosis	Treatment Other Follow-Up		
Active primary syphilis When treponemal test (Determine) is positive and non- treponemal test (RPR) has been positive for < 2 years. Treat regardless of the presence of symptoms (symptoms associated with primary syphilis: Painless, rubbery, mobile genital sores).	1 st choice: Benzathine benzyl penicillin 2.4 million IU IM single dose. Alternatives: Erythromycin 1g orally 2x per day x 14 days OR Doxycyclin 100 mg orally twice per day x 14 days	
 
Male partners should also be treated. If the woman has primary syphilis, her male partner(s) may have past, primary, secondary or neurosyphilis. For this reason, the male partner(s) should be seen by a RU Physician to determine which syphilis treatment is required. Syphilis testing of the male partner may be conducted. However, even if his tests show past instead of active infection, treatment for primary syphilis should be given because of recent exposure to the index case.
 
Couples should be treated around the same time and counseled to abstain from sex or use condoms during treatment to avoid re-infections.
 
	
Active secondary syphilis or active syphilis of unknown duration When treponemal test (Determine) is positive and non- treponemal test (RPR) has been positive for > 2 years or for unknown duration. Treat regardless of presence of symptoms (symptoms associated with secondary syphilis: generalised skin	1 st choice: Benzathine benzyl penicillin 2.4 million IU IM once a week x 3 weeks Alternatives: Erythromycin 500 mg orally 3x per day x 30 days OR Doxycyclin 100 mg orally twice per day x 30 days	
 
Ask if the participant has ever been treated in the past. However, if the treponemal and non-treponemal tests are both still positive, treat anyway regardless of past treatments.
 
Male partners should also be treated. See active primary syphilis above.
 
Couples should be treated around the same time and counseled to abstain from sex or use condoms during treatment to avoid re-infections.
 
	
lesions, many others).	Pafar to a hospital as a matter of urganou for	Mala partners should also be treated. See eating primary supplies above	
When treponemal (Determine) and non-treponemal (RPR) tests are both positive and there is neuro-muscular involvement.	intravenous Benzathine benzyl penicillin treatment.	
 
Mate pathers should also be reaced. See active primary syphilis above.
 
Couples should be treated around the same time and counseled to abstain from sex or use condoms during treatment to avoid re-infections.
 
	
Syndrome: Vaginal discharge without lower abdominal pain Conduct speculum and bimanual examination and treat only if cervical and/or vaginal discharge is seen and lower abdominal pain is ruled out.	
 
If mucopurulent discharge from the cervix or cervicitis are present: Treat for NG, CT, and TV as described above;
 
If mucopurulent discharge from the cervix or cervicitis are NOT present: Treat for BV, vaginal candidiasis, and TV as described above.
 
	
 
Partner notification and treatment is not done but women will be advised to encourage their male partner(s) to get tested themselves. To avoid social harms, we will explain to women that their vaginal discharge may be physiological and that we did not confirm the presence of an STI.
 
Women should be advised to abstain from sex or use condoms during treatment just in case they do have a STI.
 
	

 
Syndrome: Lower abdominal pain or deep dyspareunia with or without vaginal discharge (=PID)
 
RU Physician to conduct a speculum and bimanual examination; diagnose acute PID only in the case of cervical motion, uterine, or adnexal tenderness.
 
Conduct CT/NG testing.
 
Refer to the hospital in case of a missed period, recent delivery, abortion, or miscarriage, abdominal guarding or rebound tenderness, abnormal vaginal bleeding, or abdominal mass. Also refer to the hospital if the PID is severe (e.g. temp>38 ℃).
 
	
 
If PID confirmed by RU Physician:
 
Ist choice: Ciprofloxacin 500mg twice per day for 3 days AND Doxycycline 100 mg twice a day for 14 days AND Metronidazole 500mg twice a day for 14 days.
 
Add Ceftriaxone 250 mg IM single dose if the participant is NG-positive.
 
Alternatives: Ceftriaxone 250 mg IM in a single dose AND Erythromycin 1g twice per day for 14 days.
 
Alternatives: Ceftriaxone 250 mg IM in a single dose AND Tinidazole 1g per day for 14 days.
 
Alternatives: Ceftriaxone 250 mg IM in a single dose AND Erythromycin 1g twice per day for 14 days.
 
Alternatives: Ceftriaxone 250 mg IM in a single dose AND Erythromycin 1g twice per day for 14 days.
 
Alternatives: Ceftriaxone 250 mg IM in a single dose AND Erythromycin 1g twice per day for 14 days.
 
Alternatives: Ceftriaxone 250 mg IM in a single dose AND Erythromycin 1g twice per day for 14 days.
 
Alternatives: Ceftriaxone 250 mg IM in a single dose AND Erythromycin 1g twice per day for 14 days.
 
Alternatives: Ceftriaxone 250 mg IM in a single dose AND Erythromycin 1g twice per day for 14 days.
 
Alternatives: Ceftriaxone 250 mg IM in a single dose AND Erythromycin 1g twice per day for 14 days.
 
Alternatives: Ceftriaxone 250 mg IM in a single dose AND Erythromycin 1g twice per day for 14 days.
 
Alternatives: Ceftriaxone 250 mg IM in a single dose AND Erythromycin 1g twice per day for 14 days.
 
Alternatives: Ceftriaxone 250 mg IM in a single dose AND Erythromycin 1g twice per day for 14 days.
 
Alternatives: Ceftriaxone 250 mg IM in a single dose AND Erythromycin 1g twice per day for 14 days.
 
Alternatives: Ceftriaxone 250 mg IM in a single dose AND Erythromycin 1g twice per day for 14 days.
 
Alternatives: Ceftriaxone 250 mg IM in a single dose AND Erythromycin 1g twice per day for 14 days.
 
		

Diagnosis	Treatment	Other Follow-Up

 
Syndrome: Genital vesicles with or without inguinal buboes with the notion of recurrence (= genital herpes)
 
RU Physician to inspect and palpate external genitalia/inguinal area and conduct speculum exam to differentiate between the various genital ulcer/bubo syndromes and genital warts.
 
Note: herpetic vesicles are usually painful
 
	If confirmed by RU Physician: 1st (and only) choice: Acyclovir 400 mg orally 3 times per day x 7 days and 5 days in case of recurrence	
 
In female sex workers, also consider the possibility of anal genital vesicles
 
The treatment will not cure genital herpes but will reduce HSV-2 shedding and onward transmission, and may reduce the duration of the outbreak.
 
Partner notification and treatment is not indicated but the women should be adviced to abstain from sex or use condoms during outbreaks to HSV-2 transmission to sexual partner(s)
 

 
Syndrome: Genital ulcers not suggestive of genital herpes with or without inguinal buboes
 
RU Physician to inspect external genitalia/inguinal area and conduct speculum exam to differentiate between the various genital ulcer/bubo syndromes and genital warts.
 
	If confirmed by RU Physician: Treat for syphilis (as described above) and chancroid: Ciprofloxacin 500 mg orally twice per day for 3 days (Alternative: Ceftriaxone 250 mg in one single IM dose)	
 
In female sex workers, also consider the possibility of anal genital ulcers
 
Male partners should receive the same treatments.
 
Couples should be treated around the same time and counseled to abstain from sex or use condoms during treatment to avoid re-infections.
 

 
Syndrome: Inguinal buboes without ulcers
 
RU Physician to inspect and palpate external genitalia/inguinal area and conduct speculum exam to differentiate between the various genital ulcer/bubo syndromes and genital warts.
 
	If confirmed by RU Physician: Treat for chancroid (as described above) and LGV: Doxycycline 100mg twice per day for 21 days.	
 
In female sex workers, also consider the possibility of anal LGV. Anal LGV may not cause inguinal buboes but may cause proctocolitis symptoms instead.
 
Male partners should receive the same treatments. Couples should be treated around the same time and counseled to abstain from sex or use condoms to avoid re-infections.
 


 
Syndrome: Genital warts/condylomata
 
RU Physician to inspect and palpate external genitalia/inguinal area and conduct speculum exam to differentiate between the various genital ulcer/bubo syndromes and genital warts.
 
	
 
In the case of mild warts, provide treatment with 20% podophyllin solution.
 
In the case of severe warts/condylomata, refer for cryotherapy.
 
	
 
In female sex workers, also consider the possibility of anal genital warts
 
Treatment of male partners is not indicated. Women should be adviced to abstain from sex or use condoms during outbreaks to avoid HPV transmission to sexual partner(s).
 

 
Urinary tract infection
 
Do urinalysis test only when UTI symptoms are present.
 
Treat when urinalysis test shows at least 1+ leukocytes or nitrites. Also consider treatment if there is blood in urine that cannot be explained by menstrual blood or spotting related to contraceptive use.
 
	
 
1st choice: Ciprofloxacin 500 mg orally twice per day x 7 day. Alternative: Ceftriaxone IM 125 twice per day x 5 days.
 
	- No follow-up and no male partner treatment required.
Cervical cytology (not done at RU)	- Refer all high-risk women for cervical cancer screening if they have not undergone screening in the past five years.	- No male partner referral required.

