- 3. *POC testing for UTI.* Women will be asked about symptoms typically associated with UTIs; their urine will be tested by urinalysis strip if symptoms are reported; and treatment will be given as appropriate.
- 4. *POC testing for vaginal infections regardless of symptoms*. All women regardless of symptoms will be offered vaginal pH measurement with litmus paper attached to a vaginal swab to diagnose BV, POC testing for TV, and treatment for BV and/or TV as appropriate. They will also be asked about symptoms typically associated with vaginal candidiasis, and treatment based on symptom-reporting. In addition, all women will be counselled about safer sex, cessation of harmful vaginal hygiene practices, and male penile hygiene, to minimise BV recurrence.
- 5. POC testing for other curable STIs (syphilis, NG and CT) if pregnant or considered at risk by risk scoring questionnaire. The questionnaire will be developed in the beginning of the project using the behavioural factors that were most strongly associated with these curable STIs in previous RU studies. If considered at high risk by risk scoring questionnaire or pregnant, POC testing will be conducted, and treatment given as appropriate.
- 6. Treatment of genital ulcers/inguinal bubos and lower abdominal pain according to the syndromic management guidelines.
- 7. Partner notification and treatment, if applicable.
- 8. *Referrals to antenatal, HIV, family planning and other care, if applicable.*

In addition to offering these services, research activities will be carried out as follows:

- 1. To monitor and evaluate the services offered, we will collect data on monitoring and evaluation (M&E) indicators. Data for most M&E indicators will be available as part of routine clinic procedures (such as numbers of women counselled and risk scored, diagnostic tests conducted, infections diagnosed and treated, referrals made, etc.) but others will require interviewing participants at the end of their visit (client satisfaction survey), interviewing staff at the end of the study (about their experiences providing the services), timing of procedures done by different staff members, and timing of client trajectories.
- 2. To evaluate the performance of POC tests for NG, CT and TV compared to providing syndromic management alone, we will ask all women at the beginning of their visit (before any POC tests

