1.3 WISH study procedures

All participants attended a Main Visit, during which the following procedures were done in the order given: eligibility check, informed consent procedures, assignment of Patient Identification Number (PID), face-to-face interview including CT/NG and syphilis risk scoring, counselling (the participant could choose the topics she wanted to be counselled on herself), and a pelvic and bimanual examination if the participant reported relevant and moderate/severe urogenital symptoms (see paragraph 4.1, section "Pelvic, bimanual and physical examinations performed at Main and Additional Visits", for details).

Participants were offered the following additional services:

- a) Voluntary counselling and testing (VCT) for HIV.
- b) Urine pregnancy test if indicated.
- c) POC testing for UTI if UTI symptoms were present.
- d) POC testing for TV and BV regardless of symptoms, and management of vaginal candidiasis based on symptom-reporting and/or signs during a pelvic examination (if applicable).
- e) POC testing for syphilis and/or CT/NG if considered at risk by risk scoring (such as being pregnant).
- f) Syndromic management of LAP, genital ulcer syndrome (GUD) and inguinal buboes.
- g) Treatment and partner notification and treatment as appropriate, and referrals to antenatal, family planning, HIV and cervical cancer screening care.

Services were available for free at RU's research clinic for the duration of the project. Services were generally delivered within one half day. However, women could choose to leave before all results were available, and be contacted by study staff when results were available, which was particularly relevant for women undergoing CT/NG POC testing (this was performed on the Cepheid GeneXpert platform, which takes about 90 minutes).

Additional Visits took place when participants opted not to wait for test results, for partner notification and treatment, if urogenital symptoms did not resolve after treatment, and for other reasons that are summarised in this SAP. Women could notify partners themselves or allow RU staff to contact partners. They could also opt out of partner notification of specific partners, for example, if there was a risk of domestic violence. Participants who developed new urogenital symptoms were referred to local clinics because each woman was allowed to participate in the WISH study only once.

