Other sampling questions			n (%) of xxx	
Was menstruating at time of sa	mpling			

Abbreviations: BV = bacterial vaginosis; CT = *Chlamydia trachomatis*; NA = not applicable; NG = *Neisseria gonorrhoeae*; TV = *Trichomonas vaginalis*; UTI = urinary tract infection.

1. Each column contains n and % of the total number of women who had at least one AV due to a suspected ongoing untreated infection, re-infection or treatment failure. If one woman had multiple AVs related to a suspected ongoing untreated infection, re-infection or treatment failure, the data from these visits were combined.

2. May total to more than 100%. When 'other' reasons are listed, (additional) categories may be made as needed.

Syndromic diagnoses made at Main Visits and Additional Visits:

Syndromic diagnoses made by a study physician	MV ¹ n (%) N = 705	AV ^{1,2} n (%) N = xxx	Total ^{1,3} n (%) N = 705
- None			
- Genital warts/condylomata			
- Vaginal candidiasis			

- VDS – not vaginal candidiasis, tested negative for		
BV/TV/CT/NG		
- LAP (with or without VDS) - no tenderness during		
bimanual ³		
- LAP (with or without VDS) - tenderness during bimanual		
(PID)		
- Genital ulcers/blisters/sores with or without inguinal		
buboes - tested negative for syphilis		
- Inguinal buboes without genital ulcers		
- Dysuria testing negative for UTI		
- Other, specify: [additional categories to be made if		
needed]		
- Missing		

Abbreviations: AV = Additional Visit; BV = bacterial vaginosis; CT = *Chlamydia trachomatis*; LAP = Lower abdominal pain; MV = Main Visit; NG = *Neisseria gonorrhoeae*; PID = pelvic inflammatory disease; TV = *Trichomonas vaginalis*; UTI = urinary tract infection; VDS = vaginal discharge syndrome.

1. May total to more than 100% because one woman could have multiple syndromic diagnoses.

- 2. The denominator is the number of women who attended at least one AV related to a suspected ongoing untreated infection, re-infection or treatment failure. If one woman attended multiple AVs, the data from these AVs were combined. The reasons why a diagnosis was not made at the MV but at an AV will be reported in footnotes. Diagnoses made at AVs that are based on newly reported symptoms will not be included because these participants should have been referred to a local health centre.

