5.4 Overview syndromic management and WISH procedures vs. gold standard testing

An overview table will be made to compare WHO and Rwandan syndromic management, and the procedures of the WISH study, with gold standard testing.

Abbreviations: BV = bacterial vaginosis; CT = Chlamydia trachomatis; FN = false negative; FP = false positive; FSW = female sex worker; GUD = genital ulcer disease; LAP = lower abdominal pain; NA = not applicable; NG = Neisseria gonorrhoeae; PID = pelvic inflammatory disease; POCT = point of care test; Sens. = sensitivity; Spec. = specificity; TN = true negative; TP = true-positive; TV = Trichomonas vaginalis; UTI = urinary tract infection; VDS = vaginal discharge syndrome.

1. Compared to gold standard testing (CT, NG, TV, BV, candidiasis) or WISH procedures reference test (Syphilis, UTI). Sensitivity calculated by TP / (TP + FN); specificity calculated by TN / (TN + FP).

2. Under WHO syndromic management, the participant is treated for CT/NG if she is positive for VDS (with or without LAP) and/or PID. Under Rwandan syndromic management, the participant is treated for CT/NG if she is positive for VDS and (one of) her partner(s) has urethritis or she is positive for a risk score (2 or more positive of: age < 21; being single; 2 or more sexual partners in the past 12 months; new sexual partner in the last 3 months), if she has PID, or if she is an asymptomatic FSW. Under WISH procedures, the participant is offered GeneXpert CT/NG POCT testing if she is positive for the WISH CT/NG risk score previously described, and treated based on the test results. Gold standard is defined as GeneXpert CT/NG POCT performed on everyone.

3. Under WHO syndromic management, the participant is treated for BV/TV if she is positive for VDS (with or without LAP) and/or PID. Under Rwandan syndromic management, the participant is treated for BV/TV is she is positive for VDS (no matter the Rwandan CT/NG risk score described under (2)), if she has PID, or if she is an asymptomatic FSW. Under WISH procedures, the participant is offered TV OSOM POCT testing and treated based on the test results, and is offered BV by pH testing and treated based on the test results (a pH of 5.0 or higher is treated, regardless of symptoms). Gold standard testing is defined as TV qPCR, and BV qPCR vaginal health score, as explained in section 5.1

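### SAP 5.4 scores WHO and Rwandan CT/NG management by treatment but WISH by GeneXpert alone, leaving out the discharge and PID treatment routes in protocol Appendix 14.3, so WISH specificity is 100% by construction

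*Protocol*

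**What the plan says.** **Treatment guideline.** Protocol Appendix 14.3 has a row for vaginal discharge without lower abdominal pain. It applies after speculum and bimanual examination, with the instruction to "treat only if cervical and/or vaginal discharge is seen". It then has two branches: "If mucopurulent discharge from the cervix or cervicitis are present: Treat for NG, CT, and TV as described above"; otherwise "Treat for BV, vaginal candidiasis, and TV as described above". Neither branch depends on a test result. The next row treats PID found on examination. Protocol 6.2 (step 9) points to Appendix 14.3 for treatment at the Main Visit.

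**Service lists.** Protocol 4.1 limits syndromic care to "Treatment of genital ulcers/inguinal bubos and lower abdominal pain according to the syndromic management guidelines". SAP 1.3 has the same scope: "Syndromic management of LAP, genital ulcer syndrome (GUD) and inguinal buboes". Candidiasis is handled separately, as "management of vaginal candidiasis based on symptom-reporting and/or signs during a pelvic examination (if applicable". Neither list includes discharge as a syndrome.

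**What SAP 4.1 reports.** Its table of physician syndromic diagnoses has a discharge line: "not vaginal candidiasis, tested negative for" BV, TV, CT and NG. The treatment section that follows says both laboratory-confirmed and syndromic diagnoses available at the Main Visit were treated. The section on examinations says that examined women without candida signs were not treated for candidiasis.

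**Scoring.** SAP 5.1 sets out when treatment is due under each strategy. For WISH CT/NG it gives only a positive GeneXpert after risk scoring. Footnote 2 of SAP 5.4 gives WHO CT/NG treatment as discharge and/or PID. For Rwanda it gives discharge with a risk factor, PID, or asymptomatic sex work. A WISH woman is tested if risk-score positive, "and treated based on the test results. Gold standard is defined as GeneXpert CT/NG POCT performed on everyone".

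**The concern.** The first column of the SAP 5.4 table is what the woman is treated for, so a reader will take all three strategies as measured by treatment. A GeneXpert-negative woman with discharge is a false positive under WHO, and under Rwanda if she has a risk factor. If the same woman was given CT/NG treatment in WISH because of Appendix 14.3, the WISH column still counts her as a true negative. The same applies to PID treatment. The comparison can then only flatter WISH on CT/NG specificity, which is where syndromic management is expected to look worst.

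SAP 5.5 does not fill the gap. It tabulates over-treatment for TV, BV and candidiasis, but not for CT/NG.

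**Working it through.** The plan states no accuracy figure on this point, so there is nothing to reproduce. The check is the logic of the 2x2 table, followed by an illustration.

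**Step 1. WISH scoring as planned.** Index positive = risk score positive and GeneXpert positive. Reference positive = GeneXpert positive, with the assay run on everyone. Every index-positive woman is reference-positive, so FP = 0. By the SAP's formula, specificity = TN/(TN + FP) = TN/TN = 100%. PPV = TP/(TP + FP) is likewise 100%. No data can change this.

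**Step 2. Why sensitivity hardly moves.** The discharge row requires discharge seen at speculum examination. SAP 4.1 makes abnormal cervicovaginal discharge on speculum one of four criteria, any one of which turns the CT/NG risk score positive. Cervical motion or adnexal tenderness does the same, and the PID row itself calls for CT/NG testing. These women are therefore offered GeneXpert, and the infected ones are found by test unless they opt out. The syndromic routes can add essentially only GeneXpert-negative women, that is, false positives.

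**Step 3. Size on a treatment basis.** Inputs:
- N = 705 (SAP section 2).
- Expected cases per 500 women (protocol 4.3): 60 NG and 75 CT, that is 12% and 15%. Overlap is not given, so CT and/or NG lies between 15% (full overlap) and 27% (none).
- x = GeneXpert-negative women given CT/NG treatment under the discharge or PID rows. This is not in the documents. Assumed range: 5 to 70.

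Reference-negative women: 705 − 106 = 599 at 15%; 705 − 190 = 515 at 27%.

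Specificity = (reference negatives − x)/reference negatives:

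| x | 15% infected | 27% infected |
|---|---|---|
| 0 (as planned) | 599/599 = 100% | 515/515 = 100% |
| 5 | 594/599 = 99.2% | 510/515 = 99.0% |
| 20 | 579/599 = 96.7% | 495/515 = 96.1% |
| 70 | 529/599 = 88.3% | 445/515 = 86.4% |

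PPV, which SAP 5.4 does not tabulate, also needs a sensitivity. Assuming 80% gives TP = 85 at 15% infected and TP = 152 at 27%:
- x = 5: 85/90 = 94% and 152/157 = 97%.
- x = 20: 85/105 = 81% and 152/172 = 88%.
- x = 70: 85/155 = 55% and 152/222 = 68%.

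**Step 4. TV and BV.** TV is treated in both discharge branches and BV in the second; SAP 5.1 regards PID treatment under the guidelines as covering both. The WISH tests for TV and BV differ from the qPCR reference, so zero false positives are not built in. On a treatment basis sensitivity could rise (test-negative infected women treated) and specificity fall.

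**Step 5. Candidiasis.** SAP 5.3 already uses treatment given as the WISH index. The second discharge branch conflicts with the SAP 4.1 statement that examined women without candida signs were not treated. If that statement describes practice, the branch added nobody to the index.

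**The case against.** The strongest case on the other side has four parts.

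- **The endpoint is test performance.** The secondary objective compares syndromic management, testing after risk scoring and testing of everyone. SAP 5.3 scores exactly that, and the SAP says openly that GeneXpert is its own reference. This stands. A reader might infer that WISH CT/NG accuracy is mis-scored throughout; it is not. The 5.3 rows are valid as accuracy of risk score plus test. The objection does not cover 5.4, which is labelled by treatment and scores the other two columns that way.
- **No passage reports CT/NG drugs being given to test-negative women.** SAP 7.5 says observed treatment agreed with the POCT results and the SOPs. That stands against any claim that over-treatment occurred. It does not settle the matter, because SAP 7.1 says the SOPs cover treatment after syndromic diagnosis as well as after a POCT.
- **The women are not hidden.** SAP 4.1 tabulates the test-negative discharge diagnosis and the antibiotics given, and SAP 5.3 has a row for WISH PID treatment against the reference tests. True, but none of this reaches the 5.4 comparison.
- **Candidiasis.** A reader might infer that the WISH candidiasis index is inflated by women with discharge and no candida signs. The documents do not show this: SAP 4.1 says such women were not treated once examined. SAP 1.3 also allows symptoms and/or signs, and footnote 4 of 5.4 gives no WISH candidiasis rule to breach.

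The flowcharts in Appendix 14.2 and SAP 8.3 could not be read in the text reviewed, and may show where discharge sits in the WISH flow.

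**Conclusion.** The contradiction between Appendix 14.3 and the service lists and scoring rules is real. Its analytic consequence is narrow: in SAP 5.4, WISH CT/NG specificity is fixed at 100% while the WHO and Rwandan columns are charged for treating discharge and PID. The imbalance can run only in WISH's favour. It touches specificity, and PPV if derived, on a treatment basis. Sensitivity is essentially unaffected.

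For an assumed 5 to 70 women, specificity would be about 99% to 86%. That range rests on the assumed count and on the protocol's expected NG and CT frequencies; the true count could be zero. Mis-scoring of candidiasis is possible but not shown.

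**What to change.** 1. Reconcile the Appendix 14.3 discharge row with protocol 4.1, SAP 1.3 and the SAP 4.1 statement on candidiasis after examination. This review takes no view on which clinical rule is right.
2. State in SAP 5.4 whether the WISH columns are scored by test result or by treatment given.
3. Keep the test-based WISH row. Add a treated-under-WISH row for CT/NG, and for TV and BV, that includes treatments recorded under the discharge and PID diagnoses. All three strategies can then be compared on the same basis.
4. For candidiasis, keep treatment given as the index, and report separately any women treated under the discharge row without candida signs.

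The cost is SAP wording and a few cross-tabulations of diagnoses and treatments already collected. WISH CT/NG specificity may look slightly less favourable.
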